### Abstract

In Lao People's Democratic Republic (Lao PDR), tobacco smoking prevalence among cancer patients is high: 60% in men and 15% in women. Evidence from developed countries suggests that smoking cessation offers considerable benefits for cancer survivors, including improving cancer treatment outcomes, reducing recurrence rates, reducing second primary tumor development, and reducing overall cancer mortality rates. Despite, ***no tobacco treatment programs are available*** in major (public) hospitals in Lao PDR, including in cancer hospitals/institutions. The parent project (1R21CA253600-01, **OUHSC IRB#: 12189**) aims to adapt and evaluate the efficacy of our theoretically and empirically based mobile health (mHealth) technology to help Lao general patients quit smoking cigarettes. This mHealth automated treatment (AT) approach includes a fully automated, interactive, personalized, smartphone-based intervention for behavioral treatment, delivered through our Insight platform. In year 1 of the parent project, we have been adapting our intervention content to the sociocultural context, language, and communication styles of Laotians. The ***purpose*** of this supplementary project is to expand our mHealth-based AT to ***address the pressing need for smoking cessation among cancer survivors and their caregivers in Lao PDR***. In this project, we will adapt our intervention and materials to make them comprehensible and relevant to these target populations. Next, we will conduct a pilot randomized controlled trial (RCT, N=80) to evaluate the preliminary efficacy of the intervention. Cancer survivors (n=40) and caregivers (n=40) of both sexes who smoke will be recruited at Setthathirath Hospital and Lao National Cancer Center. Similar to the parent project's design, participants will be randomized to 1 of 2 treatment groups: standard care (SC) or AT (20 cancer survivors and 20 caregivers in each group). SC consists of brief advice to quit smoking, self-help written materials, and a 2-week supply of NRT (transdermal patches). AT consists of all SC components plus our fully-automated interactive smartphone-based treatment program, personalized and tailored to cancer survivors or caregivers. The ***primary RCT outcome*** is biochemically confirmed self-reported 7-day point prevalence abstinence at 3 months post-study enrollment. The ***specific aims*** are: 1) to evaluate the feasibility of AT in cancer survivors

and caregivers, and 2) to evaluate the preliminary efficacy of AT in each cancer survivor/caregiver subgroup.

### Protection of Human Subjects:

The study protocol and all related research materials (e.g., informed consent forms and assessments) will be reviewed and approved by the Institutional Review Boards (IRBs) of the Ministry of Health - Lao National Ethics Committee for Health Research (NECHR) IRB #1 (IRB00006227) and of The University of Oklahoma Health Sciences Center (OUHSC). Our collaborative hospitals—Setthathirath Hospital and Lao National Cancer Center—are under supervision/management of the Ministry of Health of Lao PDR and have assurances relying upon the NECHR IRB#.

### A. SPECIFIC AIMS

The specific aims are to:

- **Aim 1:** Evaluate the feasibility of AT in cancer survivors and caregivers. *Hypothesis (H1):*  $\geq 75\%$  of AT content will be viewed/opened as indicated by digital date/time stamp in Insight.
- **Aim 2:** Evaluate the preliminary efficacy of AT in each cancer survivor/caregiver subgroup. *Hypothesis (H2):* At the 12-week follow-up, 7-day point prevalence abstinence will be higher in the AT (vs. SC) group.
- **Aim 3 (capacity building):** Advance mHealth research capacity in Lao PDR and sustain the US-Lao PDR research network by supporting Lao investigators through in-person workshops, in-service trainings, online trainings, manuscript preparation, and future mHealth research collaboration and grant applications.

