## C2. PRELIMINARY STUDIES

Most relevant to this proposal is our most recent pilot work (with qualitative and quantitative

components) at an HIV clinic in Phnom Penh, Cambodia. We linguistically and culturally adapted the intervention for Cambodian smokers, and then conducted a pilot RCT comparing SC (n=25) to AT (n=25) delivered by our Insight™ platform. Of all scheduled notifications and weekly assessments during the 2-month treatment period, 75% were delivered properly (i.e., the phones were properly charged, turned on, and not lost). Of all delivered messages and assessments, 81% were opened, as indicated by the digital date/time stamp. Retention through the end of the 2-month treatment period, as indicated by returning to the clinic for biochemical confirmation of smoking status (expired CO) was very promising – 100% in the AT group and 92% in the SC group. The **biochemically verified 7-day point prevalence abstinence rate at 2 months was 40% in the AT group and 8% in the SC group** (RR=5.0; 95% CI: 1.2–20.5). The AT group also scored significantly better (p=0.001) on knowledge items about smoking-related health risks and had a greater, but nonsignificant, change in cessation self-efficacy. Most participants agreed that the AT program was helpful in supporting smoking cessation (92%) and would recommend it to other smokers (88%). These data demonstrate the **acceptability, feasibility, reliability, simplicity, and preliminary efficacy of our AT technology in LMICs**. This success suggests that **AT may be appropriate and efficacious in Lao PDR**, a culture comparable to Cambodia.

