## D. RESEARCH DESIGN AND METHODS

### Stage 1: Further adapt the AT intervention

[figure not shown]
Before conducting the RCT, we will use a multi-step process to adapt our already developed AT intervention for use by the target populations (i.e., cancer survivors and caregivers). These iterative steps include modifying content, user testing and eliciting feedback, and refining. Specifically, we will review all communication messages in the current AT program and modify them to ensure that they are applicable to cancer survivors and caregivers and to both sexes. Then, we will evaluate the AT content applicability, comprehensibility, and linguistic simplicity and clarity with ~10 cancer survivors or caregivers. We will ensure that approximately half of these testing users are women and that the whole testing sample is demographically diverse. Using input and feedback from these testing users, we will revise the AT further if needed. These series of tests and user-feedback sessions to refine the content further and to debug the system will go through an iterative process as needed. AT content taps on theoretical constructs of the Phase-Based Model (PBM)—a theoretical framework specific to smoking cessation used in our JITAI.

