**Figure: Study schema**

With these criteria in our Cambodian pilot study, we recruited 2–5 participants per day; thus, we expect a similarly high consent rate and feasibility for this study.

**Baseline assessment.** Enrolled participants will complete a 45-minute baseline self- or assisted interview, managed and delivered by REDCap. Participants will be randomly assigned to SC or AT by the REDCap randomization module (simple, 1:1). Smartphones will be loaned to participants as needed. All participants will complete a brief training session on smartphone use and the Insight app. The Insight app also includes a help button for instructions on how to use each feature, which participants can review at any time.

**Treatment groups.** SC consists of brief advice to quit smoking delivered by research staff, self-help written materials (the WHO’s “A guide for tobacco users to quit” that we have translated to and validated in Lao), and a 2-week supply of NRT (transdermal patches). AT consists of all SC components plus a fully automated smartphone-based JITAI that involves proactive, interactive, and personalized messages, images, or videos in Lao. Adapted from the parent study and based on the PBM, AT content is designed to increase motivation, self-efficacy, and use of coping skills and reduce nicotine withdrawal symptoms and stress. AT will begin immediately after enrollment and continue for 12 weeks (about 2 messages/images/videos per day, delivered at participants’ preferred time). Quit date is set at day 14 post-enrollment for AT and SC participants. JITAI content for AT participants each week will be **personalized and tailored** to each participant’s **baseline information** (e.g., sex, cancer types, caregiver status, and current health conditions), **current PBM phase**, and **responses to the brief weekly EMAs** that drive AT (see *Measures*). Our AT only targets cigarette smoking because it is the most common type of tobacco used by Lao smokers (95%).

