**Measures (Table).** **Primary assessments** will be conducted at **baseline and at the 12-week follow-up**, which collect 3 types of data: self-reported data collected by REDCap, expired air carbon monoxide (assessed with Vitalograph BreathCO) to verify smoking status biochemically, and medical record data (for AT personalization). Most of these measures are similar to the parent study and have been translated into Lao. Participants will be compensated US\$15 after completing each of the two primary assessments.

Participants in both groups will be asked to complete **brief weekly assessments** (EMAs)

via Insight app. AT participants will receive 6 PBM-based smoking-related questions (*Table*) that drive JITAI. To balance the effects of these weekly contacts between the RCT groups, we will ask SC participants to complete a weekly 6-item diet EMA. All participants will be provided a prepaid 3-month unlimited data plan. The **primary outcome** is biochemically confirmed (CO level <6 ppm) self-reported 7-day point prevalence abstinence.

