**Table. Trial Assessments**

Variable type	Measure	BL	W*	12
Descriptors/ potential moderators	Demographics; Health Literacy 	X		X #
	Alcohol and Drug Use 	X		X
	COVID-19–related issues,  co-morbidities 	X		X
	Dependence – Heaviness of Smoking Index 	X		
Feasibility/ Adherence to AT app	Numbers of messages/images/videos opened and completed; weekly assessments opened and completed; activity logs	Date/time stamps in Insight		
Phase-Based Model mechanisms	Wisconsin Smoking Withdrawal Scale 	X		X
	Reasons for Quitting (Intrinsic, Extrinsic) 	X		X
	Contemplation Ladder 	X	X	X
	Kessler Psychological Distress Scale (K10) 	X	X #	X
	Positive and Negative Affect Schedule 	X	X #	X
	Self-Efficacy (related to smoking cessation) 	X	X #	X
Cancer survivorship	Fear of cancer recurrence (survivors only),  family support,  and spiritual well-being 	X		X
Qualitative, open-ended assessment	An in-app participant-initiated assessment—“Share with us anything on your mind”—with an open text field to capture the participant’s thoughts, feelings, and behaviors	Initiated anytime by participant		
Primary outcome	Smoking status in the past week 	X	X #	X
	Expired carbon monoxide at follow-up 	X	X	X
Secondary outcomes	E.g., number of quit attempts, days abstinent, and other tobacco product use 	X		X

Abbreviations: AT, automated treatment; BL, baseline; W, weekly; 12, 12-week follow-up. \**Delivered via Insight app*; \*\**Brief versions of the scales*.

preliminary nature of the RCT, we do not expect to have sufficient power for full hypothesis testing. However, from our previous work, we anticipate that the abstinence at the 12-week follow-up will be 8% in the SC group. With 40 participants in each group, we will have 80% power to detect a difference as small as 20% in smoking abstinence rates between groups ( $\alpha=0.05$ , one-tailed, unadjusted).

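### Does the 75% feasibility threshold in H1 need a stated denominator?

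*Combined protocol and SAP*

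**What the plan says.** Section A gives Aim 1 one numerical criterion, H1: at least 75% "of AT content will be viewed/opened as indicated by digital date/time stamp in Insight". No denominator is named there. The Data analysis paragraph of section D and section M say only that feasibility will be summarised with descriptive statistics.

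Three other places bear on the base and the item set:

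- **Section C2 (pilot results).** Of scheduled notifications and weekly assessments, "75% were delivered properly (i.e., the phones were properly charged, turned on, and not lost". Then: "Of all delivered messages and assessments, 81% were opened, as indicated by the digital date/time stamp".
- **Section D, Stage 2 (Treatment groups and Measures).** The AT programme sends "about 2 messages/images/videos per day" for 12 weeks. Weekly assessments go to both arms: "AT participants will receive 6 PBM-based smoking-related questions", and SC participants receive a diet questionnaire of the same length. The AT answers steer the tailoring.
- **Table, Trial Assessments.** The feasibility row lists "Numbers of messages/images/videos opened and completed; weekly assessments opened and completed; activity logs", with no denominator.

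**The concern.** H1 is the only threshold attached to Aim 1, and the pilot shows that delivery and opening are separate steps, each with its own losses. If the base is not written down, one analyst could divide opened items by delivered items and another by scheduled items. At the pilot's rates they would report opposite verdicts from the same logs, and in principle the base could be picked after the logs were seen. The two ratios also answer different questions: how participants engaged with what reached them, and how much of the intended programme they saw. A second, smaller ambiguity is whether weekly assessments belong in the count, since the pilot pooled them with messages and the feasibility row names them separately.

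**Working it through.** **Inputs.** H1 threshold 75% (section A). Pilot delivery 75% of scheduled items and pilot opening 81% of delivered items (section C2). About 2 messages a day for 12 weeks and one assessment a week (section D). The document gives no opened/scheduled figure and no pilot item counts, so the two pilot rates are taken as stated. Both cover messages plus assessments, so they can be multiplied.

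**Step 1: the two bases at the pilot's rates.**

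- Opened/delivered = 81%, at or above 75%: met.
- Opened/scheduled = delivered/scheduled × opened/delivered = 0.75 × 0.81 = 60.75%: missed.
- Rounding of the inputs moves the second figure only from 0.745 × 0.805 = 60.0% to 0.755 × 0.815 = 61.5%.

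**Step 2: dependence on delivery.** Delivery in this trial is not predicted in the document. Holding opening at 81%:

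| Delivered/scheduled | Opened/scheduled | Same verdict on both bases? |
|---|---|---|
| 75% | 60.8% | no |
| 80% | 64.8% | no |
| 85% | 68.9% | no |
| 90% | 72.9% | no |
| 95% | 77.0% | yes |

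The verdicts agree from 0.75 / 0.81 = 92.6% delivery upward. At 75% delivery they differ for any opening rate from 75% to just under 100%. At the lower end, 0.75 × 0.75 = 56.25% of scheduled content would have been opened.

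**Step 3: the item set.** Messages: 2 × 84 = 168. Assessments: 12. Total: 180, so assessments are 12/180 = 6.7%. The threshold is 0.75 × 180 = 135 items.

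- All assessments opened: messages need (135 − 12)/168 = 73.2%.
- No assessments opened: messages need 135/168 = 80.4%.
- Assuming 60% to 90% of assessments are opened: (135 − 10.8)/168 = 73.9% to (135 − 7.2)/168 = 76.1%.

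The item set can therefore reverse the verdict only close to the threshold. If messages were opened at 81%, adding assessments would give between 136.08/180 = 75.6% (none opened) and 148.08/180 = 82.3% (all opened), which meets H1 either way. These counts are on the scheduled base; they carry over to the delivered base if both item types are delivered at the same rate.

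**Step 4: what the text implies.** H1 identifies opening by the Insight time stamp. Section C2 uses nearly the same phrase, there explicitly on delivered items, and H1's 75% lies a little below that 81%. A scheduled base would set the target 75 − 60.75 = 14.25 points above what the pilot achieved. The support for a scheduled base is that two sentences in section D use the term AT content for the programme as designed: "we will evaluate the AT content applicability, comprehensibility, and linguistic simplicity and clarity" and "AT content is designed to increase motivation, self-efficacy, and use of coping skills and reduce nicotine withdrawal symptoms and stress". The first concerns user testing and the second the purpose of the content; neither counts items or refers to a schedule. On the item set, section D describes AT as messages, images or videos and treats the assessments as an input. Both arms also receive weekly assessments, so these are not specific to AT. The text leans towards leaving them out.

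**The case for a change.** The strongest case for a change is that a pilot report in the background section does not define a hypothesis in this trial. H1 is labelled a hypothesis and carries a threshold, and section B1 says the results will feed a larger grant application, so a reader could fairly want its base fixed in advance. Nor can full delivery be taken for granted. Section B2 says the app works without a connection, but the pilot tied delivery to phones being charged, switched on and not lost, and it used the same platform. One clause would settle the base at almost no cost.

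Part of this stands: the denominator is not written anywhere, the arithmetic is right, and at the pilot's rates the base decides the verdict. But the remedy would ask the team to record whichever base it prefers; it would not correct a wrong rule or supply a better one. Nor would it ensure that two analysts agree. H1 also leaves open whether the percentage is pooled over items or averaged over participants, and whether it is judged overall or separately for survivors and caregivers. The worry about choosing the base afterwards is weakened by the team's own practice of reporting both component rates.

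**Conclusion.** No change to the plan is needed. H1 leaves its denominator unstated, but the delivered base is implied by the pilot wording and by where the threshold sits, and messages, images and videos are the likelier item set. The contrast of 81% with about 61% is real at the pilot's rates. It comes wholly from the base and disappears once delivery reaches 92.6% at 81% opening. The item set matters only within a few points of 75%.

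Little depends on the outcome: the primary outcome is abstinence, feasibility is descriptive, and no test, sample size or progression rule uses H1. Described as the pilot was, the logs would show delivery and opening side by side, and any reader could derive the scheduled-base figure.

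This rests on two assumptions: that the Insight logs record delivery as well as opening, as they appear to have done in the pilot, and that the team again reports the two rates separately.

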### B1. BACKGROUND AND SIGNIFICANCE

Globally, tobacco causes approximately 6 million deaths each year, of which 80% occur in low- and middle-income countries (LMICs). Tobacco use is the most important modifiable risk factor for cancer prevention and is a leading preventable cause of death; smoking prevention and cessation are the most impactful and cost-effective interventions among the many recommended evidence-based preventive health services. Despite the need, cessation treatments in LMICs are often unavailable or unaffordable for most people.

Of 7 million citizens in Lao PDR, 51% of men and 7% of women smoke tobacco. Although several tobacco control efforts have been implemented in Lao PDR (e.g., taxing tobacco products, expanding smoke-free environments, requiring health warnings on cigarette packaging, and comprehensive bans of tobacco advertising), ***no national tobacco treatment programs are available***; we confirmed this in recent discussions with leaders of the National Tobacco Control Committee (NTCC) of Lao PDR. NTCC also described a pilot quitline with telephone counseling at the national Mahosot Hospital. However, funding limitations restrict NTCC's ability to train more counselors and retain them for a nationwide implementation. Thus, ***there is a pressing need for evidence-based and highly scalable tobacco cessation treatment in Lao PDR to prevent smoking-related morbidity and mortality***. Our project will address this unmet need.

**Potential of mHealth interventions.** The World Health Organization (WHO) acknowledges that mHealth could transform the face of health service delivery across the globe, including in least-developed countries (LDCs). Data from the International Telecommunication Union, which

is the United Nation's official source for global information technology statistics, show that mobile-cellular subscriptions now make up >98% of voice subscriptions in LDCs. Active mobile-broadband subscriptions grew extremely rapidly from 4% in 2007 to 56% in 2017, without signs of faltering. Mobile-phone prices in LDCs, including Lao PDR, decreased from 29% of gross national income per capita in 2010 to 14% by the end of 2014, resulting in increased ownership rates. Worldwide, the Asia and Pacific regions have the lowest average prices of mobile phones and cellular service and the most aggressive competition in prepaid mobile-cellular service. In some LDCs in the region, including Lao PDR, prepaid handset-based mobile-broadband prices are less than 5% of gross national income per capita, making them outstanding examples for affordable mobile-broadband services in LDCs. In Lao PDR, there are 4 major mobile operators, 2 of which launched LTE in 2015. In recent years, mobile-cellular subscription rates in Lao PDR ranged from 56%–68%; half of these included mobile-broadband subscriptions. Although these subscription rates are moderate compared with the regional average, the most recent data indicate that Lao PDR was in the top 5 countries globally for increased mobile-broadband subscriptions from 2016–2017, suggesting **substantial growth in mobile-broadband coverage and usage in the near future**. Most smartphones (80%) in Lao PDR are Android-based (predominantly Samsung and Huawei) and can function in Lao script. In summary, **smartphone ownership is clearly increasing in Lao PDR, providing an ideal yet largely untapped mechanism to deliver smoking cessation treatment**.

A small but growing body of research indicates that **mHealth interventions are feasible in Lao PDR**. For example, the Lao PDR Ministry of Health (MOH) supported the use of the Safe Delivery mobile app to provide midwives with direct and instant access to evidence-based and up-to-date clinical guidelines on basic emergency obstetric and neonatal care, making childbirth safer, especially in the most remote areas. Short message service (SMS) is also used in a real-time reporting system for vaccine administration and monitoring. The MOH's receptiveness and support of mHealth solutions **increase the potential for sustainability and widespread adoption of our proposed mHealth intervention approach**.

The effectiveness of smoking cessation interventions using text messaging, traditionally delivered via SMS, is shown in both randomized controlled trials (RCT) and a recent Cochrane review. A thorough economic analysis demonstrated that a mobile phone text messaging intervention for smoking cessation is cost-effective. Indeed, mobile phone-delivered text messaging has been identified as one of the most affordable interventions and has been endorsed and used by several international organizations, including the WHO, in their global tobacco control efforts. Development and evaluation of advanced smartphone-delivered interventions are ongoing. Leading app stores house >170 English-language apps designed to facilitate smoking cessation; however, only 6 of these are scientifically grounded, and only 3 of these have demonstrated a positive impact on abstinence compared to a control condition in pilot RCTs. While the evidence base for these next generation interventions has not yet been established, many agencies such as the US National Cancer Institute have made scientifically-supported apps available for public use.

This supplementary project is **relevant and responsive** to the NOSI [NOT-CA-21-058](#) because it focuses on stimulating global cancer survivorship research using mHealth in Lao PDR—a LMIC as defined by the World Bank. Specifically, this study will evaluate the feasibility of a care/intervention delivery model beyond healthcare settings (i.e., mHealth approach) for cancer survivors (6,000 new cancer cases each year, the most common types: liver, breast, lung, and cervical-uterine) and caregivers. The study will adapt an evidence-based survivorship care service (i.e., smartphone-based smoking cessation treatment) in the United States (US) to serve these populations. This application is built on and leverages our existing relationships with stakeholders at national institutions in Lao PDR, including Setthathirath Hospital (SH), Lao

National Cancer Center (LNCC), National Tobacco Control Committee (NTCC), and the Ministry of Health (MOH). Results from this pilot project will be critical for developing our future R01 application and will contribute **significantly to reducing tobacco-related complications in cancer treatments, co-morbidities, cancer recurrence, and mortality rates in cancer survivors.**

